#### GOALS AND OBJECTIVES

### 1.1 Primary Aim

To determine the incidence of successfully achieving peripheral blood concentration of methotrexate of 50-80µM in patients at high risk of drug toxicity after a 24 hour infusion of high-dose methotrexate treated according to our institutional treatment algorithm for individualized methotrexate dosing.

### 1.2 Secondary Aims

- 1.2.1 To determine the incidence of the following side effects in high risk patients receiving high dose methotrexate as a 24 hour infusion: nephrotoxicity, neurotoxicity, mucositis, hepatotoxicity, and myelosuppression.
- 1.2.2 To describe host polymorphisms that may identify risk of methotrexate toxicity or success of this institutional protocol.
- 1.2.3 To describe predictors of successfully achieving an optimum concentration of methotrexate at the end of a 24 hour infusion of HDMTX in patients at high risk of drug toxicity treated with this individualized high dose methotrexate protocol.

### 1.3 Hypothesis

At least eighty percent of patients with a high risk for or past history of significant methotrexate toxicity, receiving 24-hour high-dose methotrexate infusions per this institutional algorithm for individualized dosing will have an appropriately therapeutic but minimally toxic 24 hour methotrexate level between 50-80µM.

#### 2. BACKGROUND

Methotrexate is a crucial chemotherapeutic agent used to treat children with acute lymphoblastic leukemia (ALL), and is a staple of treatment regimens both nationally and internationally¹. In fact, cure rates for ALL approach 80%, in part due to the incorporation of methotrexate into treatment protocols¹. While all serum concentrations of methotrexate have shown to be efficacious in ALL therapy, when doses above 1g/m² – considered high dose methotrexate (HDMTX) – are given, several leukemic cell methotrexate resistance mechanisms are readily overcome². Most current protocols using HDMTX, including those run by the Children's Oncology Group (COG) now utilize 5g/m² given as a 24 hour infusion in non-Down syndrome leukemia patients³. Many studies have demonstrated the clinical benefits of HDMTX⁴;⁵, even when directly compared to lower doses of methotrexate⁶. Recent data from the National Cancer Institute (NCI) sponsored COG trial AALL0232 compared the effectiveness of HDMTX and 6-MP against Capizzi escalating methotrexate plus PEG asparaginase (C-MTX/ASNase) in patients less than 30 years old with high-risk ALL (HR-ALL). Initial analysis showed that patients randomized to receive HDMTX had significantly higher 5-year event-free survival (EFS) compared to patients who received C-MTX/ASNase (82+ 3.4% versus 75.4 + 3.6%, p=0.006)². This finding lead to all patients with HR-ALL being treated with HDMTX.

However, treatment with HDMTX can be associated with significant toxicity. The risk of morbidity and mortality from methotrexate toxicity increases when the drug is given at high dose. Toxicities are directly correlated with increased drug exposure and since methotrexate is cleared renally, patients with kidney dysfunction are at particularly high risk of complications. In patients treated with HDMTX, 1.8% will experience renal dysfunction. Patients with relapsed ALL are at increased risk of methotrexate toxicity due to prior exposure to nephrotoxic chemotherapy, as are patients with renal injury. Per current COG protocols, patients with certain features indicating a high risk of toxicity to methotrexate will either have their methotrexate arbitrarily reduced by 25%, or it will be omitted from their treatment regimen entirely reducing or eliminating the important anti-leukemic effects of the drug.

#### 2.1 Methotrexate Pharmacokinetics

The pharmacokinetics of methotrexate vary greatly among patients, with a fixed dose resulting in a 7-fold variation in the range of plasma concentration. This variability can also exist in individual patients on subsequent administrations of HDMTX. Therapeutic drug monitoring has thus become a standard part of protocols in patients receiving HDMTX.

Typically pharmacokinetics of HDMTX are described using a two compartment model with four parameters (CL – clearance, V1 – central compartment volume of distribution, V2 peripheral compartment volume of distribution, and Q – intercompartmental clearance). Clearance (CL) of MTX ranges from 3.5-7.1 L/h, and is inversely proportional to the age of the patient. Among patients with the same total bodyweight (TBW), MTX clearance was 30% higher in children less than 10 years when compared with children greater than 10 years of age. The volume of distribution of central compartment ( $V_1$ ) is 45% of TBW regardless of age.

The variation in pharmacokinetics also has important clinical implications. Prospective pharmacodynamic studies of patients with ALL receiving HDMTX have shown that those patients with median MTX plasma concentration at steady state ( $Cp_{ss}$ ) less than  $16\mu M$  had significantly lower rates of remaining in remissions compared to patients with  $Cp_{ss}$  greater than  $16\mu M^5$ .

### 2.2 Polymorphisms

High-dose methotrexate administered as a 24 hour infusion is a standard therapy for patients with leukemia, types of lymphoma, and other malignancies. Though thousands of patients receive the same treatment, only a small subset will develop methotrexate toxicity. This suggests that individual variations in methotrexate metabolism may contribute to the development of toxicities.

Previous studies have identified several functional polymorphisms in both the folate cycle and methotrexate transporters now thought to play a significant role in the large variation in pharmacokinetics, response, and toxicity seen in patients who receive HDMTX. For example, the solute carrier 19A1 (SLC19A1, also known as reduced folate carrier 1, RLF1), is the main mechanism by which MTX enters the cell. The expression of SLC19A1 correlates with intracellular MTX concentration. Variations in the SLC19A1 gene have been shown to impact event-free survival. The most common single nucleotide polymorphism (SNP) in *SLC19A1* results in the substitution of Arg with His at position 27. Recent data have shown that this SNP is also associated with HDMTX toxicity.

Another example is found in individual variances in the enzyme methylenetetrahydrofolate reductase (MTHFR). Once MTX is transported into the cell, it is metabolized to polyglutamylated metabolites. These metabolites inhibit enzymes involved in the folic acid cycle, including MTHFR. MTHFR plays an important role in the folic acid cycle as it is responsible for catalyzing the reduction of 5, 10-methylenetetrahydrofolate to 5-methyltetrahydrofolate. A common cysteine to threonine substitution at *MTHFR* 677 results in lower enzyme activity and has been shown to be associated with decreased HDMTX clearance and increased toxicity. SNPs associated with *SLCO1B1*, an organic anion transporter polypeptide, have also been shown be involved in MTX clearance.

### 2.3 Methotrexate Toxicity

While integral to improving the survival of patients with malignancy, HDMTX can also result in severe treatment-related complications. The main side-effects of HDMTX treatment include mucositis, hepatitis, renal dysfunction, prolonged myelosuppression, CNS toxicities such as seizures and stroke-like syndromes, and dermatitis. In order to minimize these side effects, drug levels are closely monitored, and aggressive supportive care measures are standard practice. During HDMTX infusions, hyper-hydration and alkalization of urine promote efficient clearance of the drug. The tetrahydrofolic acid derivative leucovorin is given post-infusion to rescue normal DNA synthesis in non-leukemia cells minimizing myelosuppression. Leucovorin dosing is typically based on post infusion methotrexate concentrations and increased for slow methotrexate clearance.

### 2.3.1 Nephrotoxicity

As methotrexate is excreted nearly exclusively by the kidneys, methotrexate induced nephrotoxicity is a serious potential complication of treatment. The two main mechanisms of methotrexate induced nephrotoxicity involve damage to the renal tubules via either a direct toxic effect or as a result of the precipitation of methotrexate metabolites. The two main methotrexate metabolites, 7-hydroxymethotrexate (7-OH-MTX) and 2,4-diamino-N-methylpteroic acid (DAMPA), are at least six times less soluble at acidic pH than methotrexate. This decreased solubility prompted alkalinization of the urine to be a major component of methotrexate supportive care. In addition, alkalinization forces the ionization of methotrexate, a weak acid, making it more water soluble, preventing precipitation and trapping unchanged cleared methotrexate in urine for efficient elimination.

In patients receiving HDMTX, 1.8% will experience renal dysfunction resultant from HDMTX. This high risk group of patients has a mortality rate of 4.4%, greater than the mortality rate of 0.8% among patients who did not develop HDMTX induced renal dysfunction.

### 2.3.2 Neurotoxicity

Methotrexate toxicity can lead to severe neurological sequelae. Among children treated with methotrexate, 3-11% will experience either transient or chronic symptoms of neurotoxicity such as: seizures, hemiparesis, aphasia, headache, and altered mental status. However, up to 76% of patients treated with HDMTX demonstrate leukoencephalopathic changes on magnetic resonance imaging (MRI). The prevalence of leukoencephalopathy increases with each subsequent course of HDMTX. Among patients who developed leukoencephalopathy following HDMTX, 10-56% had their symptoms recur when re-challenged with HDMTX.

#### 2.3.3 Other side effects

Other common side effects of HDMTX include mucositis, hepatitis, and prolonged myelosuppression. These side effects can result in hospital admission for management of symptoms, as well as a delay in subsequent cycles of chemotherapy. Increased time between chemotherapy cycles may contribute to inferior outcomes. Delayed clearance of MTX is thought to contribute to the development of these side effects, as the time of exposure to MTX is prolonged.

### 2.3.4 Management of Toxicity

As methotrexate is primarily cleared via renal excretion, patients with underlying renal dysfunction are at an increased risk of having delayed clearance. The elevated and prolonged exposure to methotrexate that results from delayed clearance makes patients more susceptible to developing other drug related complications such as mucositis and myelosuppression.

In an effort to minimize the nephrotoxic effect of HDMTX, patients concurrently receive leucovorin, hydration, and alkalinization. If nephrotoxicity and delayed clearance develop despite these measures, two further options exist for lowering plasma methotrexate concentrations: dialysis and glucarbidase (CPDG2). After dialysis plasma MTX concentrations decrease by a median of 52% (range 26-82%). Cases of rebound increases in MTX plasma concentrations by 10-221% have been reported. Patients are also subjected to the risks of dialysis including bleeding, infection, and electrolyte disturbances. The total cost through hospital discharge for patients receiving dialysis can range from \$94,000 to \$140,000^33.

### 2.4 Rationale for Treatment Design

The incorporation of HDMTX into treatment regimens for pediatric patients with ALL has improved cure rates now approaching 80%. HDMTX has proven to be effective in treating ALL, regardless of prognostic factors such as age, immunophenotype, and genetics. HDMTX is also effective at treating other malignancies such as Burkitt's lymphoma and mixed-phenotype leukemia, among others. Recent data from the NCI-sponsored COG clinical trial AALL0232 has shown that patients with HR-ALL have significantly improved EFS when treated with HDMTX/6-MP as compared to C-MTX/ASNase. As a result of this finding, patients with HR-ALL are no longer randomized to treatment during Interim Maintenance. Instead, all patients who are able receive HDMTX during interim maintenance.

Every effort should thus be made to ensure that patients can safely receive HDMTX. As effective as it is in treating leukemia, administration of HDMTX can result in serious side effects such as renal dysfunction, neurotoxicity, mucositis, prolonged myelosuppression, hepatitis, and dermatitis. The risk of methotrexate toxicity is increased in patients with impaired renal function. Due to underlying medical conditions and prior cytotoxic chemotherapy, a subset of patients with ALL is at an increased risk of developing severe methotrexate-related toxicity. There is currently no standardized method of administering HDMTX to patients at risk in increased methotrexate toxicity. As a result, these patients are at risk of having HDMTX removed from their treatment regimen or suffering severe morbidity from its side-effects.

Prior studies, mostly at the St. Jude Children's Research Hospital (SJCRH) have shown that

individualized methotrexate protocols can be safe and effective  $^{34;35}$ . Wall and colleagues used real-time complex pharmacokinetic modeling to dose-adjust HDMTX in the treatment of patients with relapsed ALL. The group demonstrated that patients receiving HDMTX have an average clearance of 103ml/min/m²  $^{34}$ , which corresponded to a steady-state plasma concentration of (Cpss) of 65µM  $\pm$  10µM at 24 hours  $^{35}$ . In addition, 58% of their patients required dose-adjustments to achieve a Cpss within this range. None of their patients experienced severe methotrexate-related toxicity. They found that the initial methotrexate clearance was the best predictor of high methotrexate Cpss  $^{36}$ .

Based largely on the previous work at SJCRH, we developed an individualized methotrexate treatment plan as an option to safely administer HDMTX, with a target Cpss of 65 μM to patients at risk for delayed clearance and subsequent toxicity. Other options for this population would include a 25% methotrexate dose reduction or complete omission of HDMTX from their treatment. Since 2007. Texas Children's Hospital (TCH) has given patients with past history of toxicities including renal toxicities individualized methotrexate with no known increase in toxicities based on evolving versions of this treatment plan (n =14 patients; ref: personal communications with faculty members of the Texas Children's Hospital Leukemia Program). Work by Aumente, et al, demonstrated that the Monte Carlo simulated MTX concentration and means over time show a peak methotrexate concentration near hour 2, with steady state occurring near hour 6. Therefore, our treatment plan provides guidelines for HDMTX dose adjustments based on hour 2 and 6 methotrexate levels. In addition, these adjustments are based on a fixed, simple bed-side algorithm and thus avoid the need for complex pharmacokinetic modeling. Patients treated according to the algorithm may thus not need their dose altered. With this in mind, in addition to our eligibility criteria we will allow attendings to enroll patients as they deem necessary, since if the MTX Cpss is therapeutic no alterations to therapy will be made. In September, 2012, this treatment plan was formalized and approved for clinical use by the Texas Children's Cancer Center Chemotherapy Safety Committee.

In addition, despite the fact that MTX pharmacokinetics, tumor response and patient toxicities are known to vary greatly and it is known that several germline polymorphisms play a role in this variation, much controversy about the functional consequences of these polymorphisms still exists. Our study, will, by definition, isolate a population of patients with a known increased propensity for certain MTX toxicities. Because the general population minor allele frequency (MAF) is known for many of the polymorphisms known to affect MTX metabolism, this study will provide a unique opportunity to compare rates of certain of these polymorphisms in our study population to that of the general population. This may help elucidate which polymorphisms truly correlate to deficiencies in MTX metabolism. In addition, we may be able to discover which polymorphisms describe a population best suited for individualized MTX dosing.

Though many genetic targets in the folate cycle and intracellular MTX transportation have already been identified, new target genes continue to be discovered. Given that the knowledge base in this field is rapidly expanding, the decision of which polymorphisms to be tested will be determined at the time of analysis, when the study accrual has been met. Common SNPs currently thought to be involved in methotrexate metabolism, pharmacodynamics and toxicity are listed below:

Polymorphism	SNP effect	Approximate MAF (%)	Clinical effect	Reference
MTHFR 677C>T	Reduced activity	15-25	Both increased and decreased risk of myelosuppression reported	37;38
SLC19A1 80G>A	Reduced activity	30-50	Increased hepatotoxicity	39
MTHFR 1298A>C	Reduced activity	15-20	Decreased myelosuppression	40
TYMS 28-bp triple repeat	Increased transcription	40-50	None reported	41

This research does not qualify for an IND as the use of HDMTX is per standard of care treatment of ALL, and the route of administration or dosage level does not significantly increase risk to the patient.

### 3. STUDY ENROLLMENT AND PATIENT ELIGIBILITY

### 3.1 Study Enrollment

### 3.1.1 IRB approval

Approval for the use of this protocol by the individual institution's Human Subjects Review Committee must be obtained, in accordance with the institutional assurance policies of the U.S. Department of Health and Human Services.

### **3.1.3** Timing

Study enrollment must take place prior to patients receiving methotrexate dose modifications.

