#### REGULATORY

- 3.2.8 Informed consent for participation in this study must be obtained within 30 days from the start of HDMTX on this protocol and prior to any research procedures from the patient and/or the patient's legally authorized guardian in accordance with institutional policies approved by the U.S. Department of Health and Human Services
- 3.2.9 All institutional, FDA, and NCI requirements for human studies must be met.

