### **Concomitant Medication Restrictions:**

- 1. Sulfamethoxazole and Trimethoprim (SMX-TPM); synonyms: Bactrim, Co-trimoxazole
- 2. Non-steroidal anti-inflammatory medications (NSAIDS)
- 3. Penicillins
- 4. Proton pump inhibitors
- 5. Aspirin-containing medications

Hold the above medications on the day of HDMTX infusion and for at least 72 hours after the start of the HDMTX infusion and until the MTX level is less than 0.4µM (In the presence of delayed clearance continue to hold these medications until MTX level is less than 0.1 µM):

As per the Children's Oncology Group (COG) and institutional guidelines, restricted medications should be stopped (i.e. 1. Sulfamethoxazole and Trimethoprim (SMX-TPM); synonyms: Bactrim, Cotrimoxazole; 2. Non-steroidal anti-inflammatory medications (NSAIDS); 3. Penicillins; 4. Proton pump inhibitors; 5. Aspirin-containing medications), and prior to receiving HDMTX patients will receive IV hydration with D5  $\frac{1}{4}$  NS with NaHCO $_3$  3 mEq/100 mL at 200 mL/m $^2$ /hr for a minimum of 2 hours, until urine pH  $\geq$  7.0 and  $\leq$  8.0 and urine specific gravity  $\leq$ 1.010.

Once these parameters are met, between hours 0-1 of the protocol patients will receive methotrexate 500 mg/m² in D5  $\frac{1}{4}$  NS with NaHCO3 3 mEq/100 mL at 200 mL/ m² IV over 60 minutes. This will be followed immediately by Hours 1 to 24 Methotrexate 4500 mg/m² in D5  $\frac{1}{4}$  NS with NaHCO3 3 mEq/100 mL 4600 mL/ m² IV at 200 mL/m²/hr for 23 hours.

Dose adjustments will be made based on the following tables. Adjustments should be made as soon as possible after MTX levels checked are resulted. Interventions are expected to be done within 120 minutes of sending the MTX level.

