The interventions in this protocol occur at the 2 and 6 hour (or 8 hour if the 2 hour level was  $\geq 100 \mu M$ ) time points. After the 24hr HDMTX infusion is complete, the individualized protocol will end and patients will remain on study but be off of the protocol therapy. After this time, management of MTX levels will continue according the treating physician's discretion using standard supportive care guidelines. This is elaborated below in Appendix B, suggested supportive care guidelines based on the COG algorithm. Interventions for toxicity are at the discretion of the treating provider as patients will be off treatment protocol at the 24hr time point. Glucarpidase should be administered based on the treating physician's discretion, with the recommendation that it be administered prior to the development of grade 4 nephrotoxicity and prior to 96 hours after the start of the HDMTX infusion. Administration of CPDG2 after these time points have been shown to be statistically associated with the development of  $\geq$  grade 4 toxicity.

Patients may be re-enrolled on this protocol therapy again for subsequent HDMTX infusions without the need for re-consent. In order to re-enroll, call the study coordinating center as outlined in Section 3.1 PRIOR to the cycle in which the dose modification protocol will be implemented.

The active length of study participation for each patient is 4 weeks after the last high-dose methotrexate infusion or until the next cycle of chemotherapy begins (which ever occurs first). Therefore, the maximum amount of active time on study would be 2.5 months. This would include 4 doses of HDMTX given every other week plus a 4 week follow-up period to assess for side effects.

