#### 9.2 Patient Accrual and Expected Duration of Trial

Patients will be continually accrued until a target of 50 methotrexate infusions requiring any protocolprescribed dose adjustments are reached. The expected duration of accrual for the trial is 2-2.5 years.

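### Section 3.1.3 does not bar first registration after an early methotrexate level is known; the deadline should be the start of the infusion (hour 0)

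*Combined protocol and SAP*

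**What the plan says.** **First entry.** Section 3.1.3 reads: "Study enrollment must take place prior to patients receiving methotrexate dose modifications". No other section states a deadline for first enrolment. Section 3.1.2 makes enrolment a weekday, office-hours telephone call, which is a separate act from consent.

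**When modifications happen.** Section 4.1 states: "The interventions in this protocol occur at the 2 and 6 hour" marks, with hour 8 replacing hour 6 after a high 2-hour level. On speed it adds: "Interventions are expected to be done within 120 minutes of sending the MTX level".

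**Repeat entry.** For later infusions Section 4.1 tells the site to "call the study coordinating center as outlined in Section 3.1 PRIOR to the cycle in which the dose modification protocol will be implemented".

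**Consent.** Section 3.2.8 requires consent "within 30 days from the start of HDMTX on this protocol and prior to any research procedures". Section 5.4 classes the 2-, 6- (or 8-) and 24-hour levels as required for research.

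**Use outside the study.** Section 2.4 reports that in September 2012 "this treatment plan was formalized and approved for clinical use". The same section lets attending physicians enrol patients at their discretion.

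**Endpoint and accrual.** Section 9.1 ties the primary endpoint and the sample size to each patient's first cycle. Section 9.2 continues accrual "until a target of 50 methotrexate infusions requiring any" adjustment prescribed by the protocol.

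**The concern.** The 2-hour and 6-hour levels are early readings of the concentration that defines success at hour 24. If a patient can be registered, or quietly not registered, after one of them has been reported, entry may depend on a precursor of the outcome. The success rate would then describe a selected group. The aim and hypothesis in Sections 1.1 and 1.3 concern high-risk patients managed by the algorithm from the start of the infusion.

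Two features make the wording worth attention. The stricter before-the-cycle rule covers only repeat infusions, so the looser rule applies to the first cycles that form the primary result. And only an adjusted infusion moves accrual towards its target. No analysis can recover patients who were never registered, so the protection has to come from the entry rule.

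**Working it through.** **Step 1. Where the deadline falls.** Inputs: Sections 3.1.3 and 4.1.

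- 2-hour level at or above 100 µM: the first modification follows that result, with action expected by about hour 2 + 2 = 4. Registration could come after the result and before the change.
- 2-hour level below 100 µM, 6-hour level at or above 75 µM: the first modification follows the 6-hour result, by about hour 6 + 2 = 8. Both levels could be known at registration.
- Neither threshold reached: no modification occurs, so Section 3.1.3 sets no effective deadline.

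**Step 2. What other sections close, and what they leave.**

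- Consent must precede research procedures (3.2.8), and the 2-hour level is one (5.4). A study draw should therefore follow consent. But a patient who has consented may still be waiting for the registration call.
- A nuclear GFR and baseline laboratory tests must precede the first on-protocol dose (5.2). This shows that work-up came first, not that registration did.
- The algorithm is approved for clinical use (2.4). If a patient is being treated that way, the early level could be ordinary care rather than a research procedure. The documents do not say how often this happens.
- The 30-day consent window in 3.2.8 does not say whether it runs before or after the start of HDMTX.

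**Step 3. The plan's own precision.** Section 9.3 uses n = 50 and p = 0.80. The Wald interval is 0.80 ± 1.96 × √(0.80 × 0.20 / 50) = 0.80 ± 0.111, or 0.689 to 0.911, width 0.222. This reproduces the stated 69% to 91% and width 0.22. No figure in the plan is disputed.

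**Step 4. How large a shift could be.** Let f be the share of infusions adjusted, and pA and pU the success rates in adjusted and unadjusted infusions. With everyone registered, the rate is f·pA + (1 − f)·pU. If only adjusted infusions are registered, it is pA. The shift is

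pA − [f·pA + (1 − f)·pU] = (1 − f)(pA − pU).

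The only figure for f in the documents is 58%, from the earlier relapsed-ALL study cited in Section 2.4. The success rates are assumptions.

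- pA = 0.80, pU = 0.60: all registered, 0.58 × 0.80 + 0.42 × 0.60 = 0.716; adjusted only, 0.800. Shift +8.4 points.
- pA = 0.60, pU = 0.80: all registered, 0.58 × 0.60 + 0.42 × 0.80 = 0.684; adjusted only, 0.600. Shift −8.4 points.
- pA = pU: shift 0.

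Over a range of f, with the same 20-point difference:

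| f | (1 − f) × 20 points |
|---|---|
| 0.30 | 14.0 |
| 0.58 | 8.4 |
| 0.80 | 4.0 |

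The shift is proportional to the difference, so a 10-point difference at f = 0.58 gives 4.2 points.

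Partial selection gives less. If unadjusted infusions are registered half as often as adjusted ones, the adjusted share among those registered is 0.58 / (0.58 + 0.42 × 0.5) = 0.734. The shift is then (0.734 − 0.58) × 20 = 3.1 points.

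**The case against.** The strongest reply is that the protocol as a whole places entry before the infusion. Eligible patients are those who will receive HDMTX (3.2.2). The loading hour is counted as the first hour of the protocol (4.1). Baseline tests sit under study entry and precede the first on-protocol dose (5.2). Consent comes before a research draw. Weekday telephone enrolment and a 120-minute window leave little room for mid-infusion entry. All of this stands, and it confines the gap to two routes: late registration of a patient who has already consented, and entry of a patient already treated under the clinically approved algorithm. It does not supply the missing deadline.

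The reply is also right on three stronger readings that a reader might infer:

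- *That entry dependent on the level is intended or rewarded.* Nothing says so. Section 9.2 is a stopping target. It does not remove unadjusted infusions from the success analysis, and Section 2.4 expects some patients to need no change. A patient registered before hour 0 contributes the same adjusted infusion, so waiting gains nothing for a patient already identified.
- *That late entry would let the trial close with 50 infusions where about 87 would otherwise be needed (50 / 0.58 = 86.2, rounded up).* Repeat infusions must be registered before the cycle, so late entry could affect first enrolments only.
- *That the result is biased by 8 points in a known direction.* The success rates are assumed and the sign can go either way. The 58% comes from real-time pharmacokinetic modelling, not from this fixed bedside algorithm.

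**Conclusion.** The point holds as a gap in the wording of the first-enrolment rule. Section 3.1.3 does not bar registration after an early level is known, it is looser than the rule for repeat entries, and it governs the first cycles that carry the primary endpoint. The rest of the protocol makes such entry narrow but not impossible.

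The documents fix neither the size nor the direction of any bias. If only adjusted infusions were registered, the shift would be (1 − f) times the difference in success rates: about 8 points either way at f = 0.58 with an assumed 20-point difference, against the plan's margin of about 11 points, and zero if the rates are equal. That is the extreme for this pattern, because it supposes that every first entry depends on the level. The amendment is justified because it removes the possibility at almost no cost, not because a bias has been shown.

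**What to change.** 1. Section 3.1.3: require that registration be complete before the start (hour 0) of the HDMTX infusion, for first and repeat entries alike. This brings it into line with Section 4.1.
2. Section 3.2.8: state that consent is obtained within the 30 days before the start of HDMTX, keeping the condition that it precede research procedures.
3. Sections 9.1 and 9.3: state that every first-cycle infusion registered before hour 0 enters the primary analysis whether or not it is later adjusted, and that later infusions enter the repeated-cycle analysis.

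The accrual target in Section 9.2 need not change for this point. Once registration precedes hour 0, no level from that infusion is known at entry, so it cannot steer who is registered.

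The cost is a short amendment in three places. No dose, treatment rule or stated figure changes. A few patients identified only during an infusion would enter the study at a later one.
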